In a recent NIDA funded preclinical study (NIDA Study Report 1812-12132, Sep. 20, 2013), lorcaserin was administered to rodents in combination with cocaine without any significant toxicity. Final results of this study are summarized here and provided in detail in an attached document. In short, at human equivalent doses in rats (i.e., 5 mg/kg, equivalent to 20 mg/day in humans, based on systemic exposures), there were no additive/synergistic effects of PO lorcaserin on IV cocaine-induced mortality or convulsions. However, at 5-fold higher doses (i.e., 25 mg/kg in rats, equivalent to 100 mg/day in humans – substantially beyond what is proposed in this study), there are indications of increased sensitivity to cocaine-induced convulsions due to lorcaserin. The combination of lorcaserin and cocaine has not been studied in humans. We will guard against potential toxicity of cocaine combined with lorcaserin by dosing cocaine using an ascending dose approach, and we have specific stopping criteria in place to stop the cocaine dose escalation if warranted by excessive cardiovascular responses. If in spite of these precautions cocaine toxicity is observed (significant hypertension, tachycardia, symptoms of ischemia or evidence of arrhythmias) we have established treatment protocols in place and a code team will respond if needed. We have never required such assistance in the past. Moreover, additional blood samples will be drawn 4-6 hours on the days of escalating cocaine infusions to measure high-sensitivity troponin I (hsTnI) and N-terminal pro-brain natriuretic peptide (NT-pro-BNP). Although not routinely utilized in clinical practice, these markers will be stored for batch analysis upon completion of the study to detect the presence cardiac strain and/or stress to the myocardium related to cocaine in the absence of overt clinical disease (Gaggin and Januzzi, 2014; Gualandro et al., 2014). This data will be used as a potential biomarker of subclinical effects of cocaine on heart for future clinical trials. The total amount of blood for the entire study will not exceed 550ml in an 8 week period.

Potential Risks Not Due to Study Medication

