Up to 18 eligible patients will be randomly assigned to lorcaserin or placebo treatment groups in a 1:2 ratio using a SAS-based computer-generated randomization scheme developed by the study data management provider.

Blinding

Due to the objectives of the study, the identity of test and control treatments will not be known to investigators, research staff, or patients. The following study procedures will be in place to ensure double-blind administration of study treatments.

Access to the randomization code will be strictly controlled.

Packaging and labeling of lorcaserin and placebo will be identical to maintain the blind.

Lorcaserin concentrations will not be analyzed till the end of the study.

The study blind will be broken on completion of the clinical study and after the study database has been locked.

During the study, the blind may be broken only in emergencies when knowledge of the patient's treatment group is necessary for further patient management. Unblinding will occur by the PI contacting the research pharmacy to break the blind in case of emergency.

Formulation of Test Product

Lorcaserin HCL 10mg tablets (Belviq, Arena Pharmaceuticals) will be used for this study. To ensure blinding, tablets will be placed in gelatin capsules by the research pharmacist prior to administration.

Commercially available sterile normal saline for human use will be used as a matched placebo for cocaine. Cocaine is packaged in 2 mL vials containing 20 mg per mL.

Cocaine for IV human use will be obtained from a NIDA contractor under a letter of authorization to allow cross reference to NIDA's DMF for cocaine obtained and submitted to the IND.

The pharmacist will prepare the cocaine according to instructions supplied by the NIDA contractor and dispense according to the randomization. The labels on the cassettes of cocaine and matching placebo will conform to internal Pharmacy and CRSU SOPs and instructions.

The doses of cocaine will be prepared by diluting cocaine with 20 mL normal saline.

Cocaine administration: Cocaine will be administered by a study nurse under the direct supervision of a physician. The drug is given intravenously (IV) over a 2 minute period in a cassette via a pump delivery system.

Formulation of Control Product

Gelatin placebo capsules identical to capsules that enclose the study drug will be used for placebo. Dextrose powder will be used as a filling in the capsules.

Packaging and Labeling

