The subject would make a series of choices using the PR schedule between ascending value money options (\$5) or cocaine (0 mg or 25 mg/i.v. infusion) using a patient controlled (PCA pump). Choices for money will be verbally indicated to the investigator. Infusions will be made over a 2 min period followed by a 13 min time-out period. Subjects will receive the cash or cocaine doses (0 or 25 mg) immediately after they meet the progressive ratio criteria for each choice, providing vital signs remain within the preset intervals. If the subject chooses all cocaine options in the cocaine choice session and no money, they will receive a maximum of 120 mg cocaine, i.v. Money choices will be given directly to the patient after choice session, but this can only be spent after departing from the CRS. All infusions on this day will be double-blinded and counterbalanced in their presentation among subjects.

Cardiovascular Monitoring During Cocaine Infusions and Cocaine Self-Administration Procedure

Cardiovascular monitoring by continuous measuring heart rate/ECG and blood pressure starting 15 minutes prior to each of the 4 cocaine infusions and continued for at least 60 minutes following each dose. PI/Co-I or their medically qualified designees will be present during all cocaine infusions to monitor and intervene if necessary. For the sessions of cocaine infusions on Day 1, 2, 6, and 10, non-invasive monitoring of cardiac hemodynamics will be performed with the NexFin finger cuff system (Edwards Life Sciences).

Criteria for withholding Cocaine Administration

Cocaine administration will not be initiated if:

- Clinically significant arrhythmias
- Resting pulse > 130 bpm
- QTc increase of greater than 30ms over baseline
- Blood pressure above 165mm Hg systolic and 100mm Hg diastolic.
- Behavioral manifestations of cocaine toxicity (agitation, psychosis, inability to cooperate with study procedures).

If cardiovascular measures have not returned to acceptable levels (heart rate <130 bpm, diastolic pressure <100mmHg, and systolic pressure <165 mmHg, QTc <30ms over baseline), the next session will be delayed by 15 min, after which these measures will be repeated.

Stopping Criteria for Subject Participation

Subject participation will be terminated if any of the following events occur:

The following values do not return to acceptable limits within appropriate time frames (approximately 30 minutes);

- Systolic BP > 180 mm Hg
- Diastolic BP > 120 mm Hg

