
[contact]

[contact], [name]

DISCONTINUATION AND REPLACEMENT OF SUBJECTS

Early Discontinuation of Study Drug

A subject may be discontinued from study treatment at any time if the subject, the investigator, or the Sponsor feels that it is not in the subject's best interest to continue. The following is a list of possible reasons for study treatment discontinuation:

Subject withdrawal of consent (or assent)

Subject is not compliant with study procedures

Adverse event that in the opinion of the investigator would be in the best interest of the subject to discontinue study treatment

Protocol violation requiring discontinuation of study treatment

Lost to follow-up

Sponsor request for early termination of study

Positive pregnancy test (females)

Chest discomfort or shortness of breath consistent with ischemia

Systolic BP > 180 mmHg

Diastolic BP > 110 mmHg

Heart rate > Maximum predicted heart rate ($> 220 - \text{age} \times 0.85$) bpm.

If a subject is withdrawn from treatment due to an adverse event, the subject will be followed and treated by the Investigator until the abnormal parameter or symptom has resolved or stabilized.

All subjects who discontinue study treatment should come in for an early discontinuation visit as soon as possible and then should be encouraged to complete all remaining scheduled visits and procedures.

All subjects are free to withdraw from participation at any time, for any reason, specified or unspecified, and without prejudice.

Reasonable attempts will be made by the investigator to provide a reason for subject withdrawals. The reason for the subject's withdrawal from the study will be specified in the subject's source documents Refer to Section 10 for early termination procedures.

Withdrawal of Subjects from the Study

A subject may be withdrawn from the study at any time if the subject, the investigator, or the Sponsor feels that it is not in the subject's best interest to continue.

All subjects are free to withdraw from participation at any time, for any reason, specified or unspecified, and without prejudice.

Reasonable attempts will be made by the investigator to provide a reason for subject withdrawals. The reason for the subject's withdrawal from the study will be specified in the subject's source documents.

Replacement of Subjects

Subjects who withdraw from the study treatment will be replaced.

Subjects who withdraw from the study will be replaced.

Protocol Violations

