Children as defined by NIH (age 18-21 years) will be included in this research. The incidence of severe cocaine abuse/dependence is relatively small in the population of youth less than 18 years old. From a safety perspective, risks of exposure to the proposed study medication and cocaine administration in substance-dependent children under 18 have not been established.

Analysis of Primary Endpoint

1. Safety: Heart rate (HR) and blood pressure (BP) measures during saline infusions will be compared to HR and BP after each cocaine infusion (20 mg and 40 mg doses). Changes in HR and BP induced by cocaine infusion along with lorcaserin will be compared to those without lorcaserin, by cocaine dose level (20 mg and 40 mg doses), using repeated measures analysis of variance (ANOVA). Changes in ECG readings during saline infusion as compared to those taken during cocaine infusions will be reported as summary statistics. Adverse event data will be compiled for lorcaserin and placebo cohorts and presented as summary statistics.
2. Cocaine Self-administration: Repeated measures ANOVA with cocaine dose (0mg, 25mg) and lorcaserin dose (0mg, 10mg, 20mg) as within subject factors will be used to examine differences in mean cocaine choice selection. In addition, a Bayesian analysis will be carried out as described below.
3. Subjective response to cocaine: Subjective response measures (VAS) obtained during saline infusions will be compared between lorcaserin and placebo subjects to those during cocaine infusions by cocaine dose level to determine the extent to which these measures are modified by the administration of lorcaserin using repeated measures ANOVA.
4. Cocaine PK: Plasma concentration-time profiles of cocaine after cocaine infusion during placebo administration (Day 2) will be analyzed to obtain pharmacokinetic parameter estimates of cocaine (Tmax, AUC, apparent t_{1/2}, CL) by individual. These parameters will be compared within subjects on sessions with lorcaserin (Day 6 and 10).

Analysis of Secondary Endpoints

Response inhibition: Commission errors on the IMT will be compared between lorcaserin and placebo subjects to determine the extent to which this measure is modified by the administration of lorcaserin using repeated measures ANOVA.

Safety and tolerability data will be summarized by treatment group.

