Adverse event rates will be coded by body system and MedDra classification term. Adverse events will be tabulated by treatment group and will include the number of patients for whom the event occurred, the rate of occurrence, and the severity and relationship to study drug.

Interim Analysis

When approximately 50% of patients have completed the study, an interim analysis for safety will be conducted by the DSMB. Serious adverse events will be monitored by the committee on an ongoing basis throughout the study.

Sample Size and Randomization

This project requires a final sample size of 18 subjects (Six subjects assigned to Group A (placebo) and 12 subjects assigned to Group B (active lorcaserin)). This sample size for effect of lorcaserin on cocaine self-administration was based on previous research showing effects of medication on human cocaine self-administration (Hart et al, 2008). In an effort to increase the power of the study, a Bayesian approach will also be utilized that incorporates information from previous studies. This approach will use a Bayesian hierarchical model with subject at the lowest level of the hierarchy and treatment group at the second level. This model is analogous to the repeated measures ANOVA except that prior information will be introduced. Since many similar studies have been conducted with cocaine users and the same outcome measures we will assign an

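### Subjects can be removed or denied a dose on the primary safety outcome itself, are then replaced, and no analysis set or missing-data rule is given; if lorcaserin adds to the cocaine response, a complete-case ANOVA would understate the interaction

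*Combined protocol and SAP*

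**What the plan says.** - **Removal.** Under Stopping Criteria for Subject Participation: "Subject participation will be terminated if any of the following events occur". The events are systolic pressure above 180, diastolic above 120, a heart-rate formula, or QTc above 470 ms, where the value has not recovered in about 30 minutes. Subjects must also go on meeting the other inclusion criteria. Early Discontinuation of Study Drug lists systolic above 180, diastolic above 110 and a heart-rate limit among possible reasons to stop treatment, with no recovery window.
- **Withheld doses.** Risks of Lorcaserin Combined with Cocaine states: "we have specific stopping criteria in place to stop the cocaine dose escalation if warranted by excessive cardiovascular responses". Criteria for withholding Cocaine Administration sets limits of 165/100 mm Hg, pulse 130 and a 30 ms QTc rise, with a 15-minute delay and recheck. In the self-administration sessions the chosen option is given "providing vital signs remain within the preset intervals".
- **Replacement.** Replacement of Subjects says "Subjects who withdraw from the study treatment will be replaced" and "Subjects who withdraw from the study will be replaced". Neither sentence carries an exception.
- **Numbers.** Sample Size and Randomization: "This project requires a final sample size of 18 subjects". Method of Assigning Subjects to Treatment Groups: "Up to 18 eligible patients will be randomly assigned".
- **Analysis.** Analysis of Primary Endpoint, item 1: "Changes in HR and BP induced by cocaine infusion along with lorcaserin will be compared to those without lorcaserin", by cocaine dose level, using repeated measures ANOVA. Data Sets Analyzed covers baseline comparisons and covariates but defines no analysis set. No missing-data rule appears in the statistical section. A detailed SAP is promised before the final analysis.

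**The concern.** The same measurements serve as primary outcome and as grounds for removal or a withheld dose. A subject stopped on Day 6 has no Day 10 session, and a subject whose pressure stays high after 20 mg has no 40 mg reading that day. Repeated measures ANOVA conventionally needs the full day-by-dose grid, so these subjects would leave the comparison.

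Days 1 and 2 are placebo for everyone, so losses there cannot differ by treatment. Losses from Day 6 on can. The protocol itself notes a modest blood-pressure increase with lorcaserin in other populations. If lorcaserin adds to the cocaine response, the lorcaserin arm loses more of its high values and the difference shrinks. Replacement does not cause this. It restores the count and makes the loss harder to see. At stake is the main safety reading of a study that describes the lorcaserin-cocaine combination as not yet studied in humans and is meant to inform go/no-go decisions for phase II.

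**Working it through.** **1. The plan's own figure.** The 18 comes from a power table (6 placebo, 12 lorcaserin; t-test power 0.138, 0.528, 0.981 and 0.999 at 10, 25, 50 and 75% change). Alpha, mean and SD are not given. Assuming two-sided 0.05 and solving the 25% column gives d = 1.08. The noncentrality is then 1.08 × √(6×12/18) = 2.16 on 16 df. Scaling d to the other columns gives 0.129, 0.528, 0.982 and 1.000, so the row is self-consistent. It does not address who is lost.

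**2. Does the cap of 18 fit replacement?** Let q be the chance that a lorcaserin subject is removed (assumed). P(at least one of 12) = 1 − (1 − q)^12, and the number to randomise for 12 remaining is 12/(1 − q), rounded up. The total adds 6 placebo subjects with none lost.

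| q | P(at least one) | Lorcaserin randomised | Total |
|---|---|---|---|
| 5% | 46% | 13 | 19 |
| 10% | 72% | 14 | 20 |
| 20% | 93% | 15 | 21 |

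One replacement is enough to break the cap, if replacements are randomised in the same way.

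**3. Size of the understatement.** Only the 180 mm Hg limit is from the documents. The assumptions are: pre-dose systolic mean 125 (SD 9); rise at 40 mg of mean 25 (SD 10) or 35 (SD 12); session SD 6; true lorcaserin excess 10 mm Hg on Day 10, with between-subject SD 5 to 10; immediate removal above 180, including on Days 1 and 2; 400,000 simulated subjects per scenario. The quantity estimated is

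(Day 10 rise − Day 2 rise) on lorcaserin minus the same on placebo.

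| Who is lost | Estimate when truth is 10 mm Hg |
|---|---|
| Any breach on Day 6 or Day 10 | 6.7 to 9.4 |
| Day 6 breaches only; Day 6 effect equal to Day 10's | 7.6 to 9.7 |
| Day 6 breaches only; Day 6 effect half of Day 10's | 9.2 to 9.9 |

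The shortfall therefore runs from 10 − 9.9 = 0.1 to 10 − 6.7 = 3.3 mm Hg.

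**4. No effect.** With no lorcaserin effect in any subject the bias is about 0. With mean effect zero but between-subject SD 8, it is −0.3 (mean rise 25) to −0.8 mm Hg (mean rise 35).

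**5. Which readings would exist.** In the example dosing diagram, 40 mg is either the last infusion or is followed only by saline. A breach after 40 mg on Day 10 therefore loses no cocaine-dose reading, though it can lose the saline reference if saline was still to come. A breach on Day 6 can lose the whole of Day 10. The first row of the step 3 table applies if a replaced subject is left out altogether; the other two apply if readings up to removal are kept.

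**The case against.** The strongest reply is that the harmful step is never written down. A reader might infer that the trial will analyse 18 completers. The text says only a final sample size of 18, and nothing says that data from replaced subjects are discarded. Subjects who stop treatment are encouraged to attend remaining visits, so some later data may exist, and the promised SAP could settle the matter. This stands as far as it goes: complete-case analysis is what the named method conventionally does, not what the plan declares. But none of it supplies the missing rule.

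A reader might also infer that the ANOVA understates the interaction whatever the truth. It does not: with no lorcaserin effect there is essentially no bias. Removal may also be rarer than simulated, because the mandatory rule has a 30-minute recovery window and the list without a window gives only possible reasons. The simulation removes at once, so its larger shortfalls are more likely too large than too small.

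A third tempting inference is that a pressor effect would pass as reduced self-administration. The documents do not support a size or a direction. The planned outcome is mean choice selection, the vital-sign condition acts on delivery after the ratio is met, and as worded it covers cash as well as cocaine. What stands is that scoring of a blocked or unoffered choice is not defined.

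Adverse events are tabulated by group, withdrawal reasons are recorded and the DSMB reviews retention, so removals would not be invisible. That does not correct the heart-rate and blood-pressure estimate. The additional Bayesian hierarchical model is described for self-administration only.

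**Conclusion.** The concern holds in conditional form. Removal and dose withholding depend on a primary outcome, replacement is unconditional, and the named analysis comes without an analysis set or missing-data rule. If lorcaserin raises the pressor or heart-rate response to cocaine and incomplete subjects are dropped, the interaction is understated. Under the stated assumptions a true 10 mm Hg excess appears as roughly 7 to 9.9 mm Hg, nearest the truth when Day 10 trigger readings are kept and the Day 6 effect is smaller. The size cannot be derived from the documents, because removal rates and the spread of responses are not given. Up to 18 randomised and replacement to a final 18 cannot both hold once a randomised subject is replaced. No bias is claimed for the self-administration outcome.

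**What to change.** Write into the SAP, before unblinding:

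- **Analysis set.** All randomised subjects who received study drug, replaced or not, with replacements counted as additional. Reconcile this with the limit of up to 18 randomised, and say how a replacement is allocated.
- **Model.** A likelihood-based mixed model for heart rate and blood pressure with arm, day, cocaine dose and their interactions. Use every available reading, including those that triggered removal. These matter because the method relies on the reason for missingness being in the recorded data.
- **Reporting.** Stops and withheld infusions by arm, day and dose, alongside the primary safety result.
- **Choices.** Count a choice when the ratio is completed, delivered or not. Treat trials not offered because of vital signs as missing.

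The two lists of cardiovascular limits also need reconciling, since they determine who is lost: diastolic 120 against 110, and a recovery window in one list only. This review takes no view on which is right.

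The cost is SAP wording and a slightly more complex model. No new measurements are needed, and no patients beyond the replacements already planned.

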Each pill bottle of study drug will be labeled with the required FDA warning statement, the protocol number, a treatment number, the name of the study physician, and directions for patient use and storage.

Administration of Study Drug

Dosage/Dosage Regimen

If subjects meet inclusion criteria, they will be seen both in the hospital and at IDAS clinic for a total of 12 active study days and monitoring procedures will be in place to detect drug and alcohol use and assess for adverse events at each visit. In addition, the hospital cocaine administration procedures will reduce the likelihood of increased cocaine craving after cocaine administration. Subjects will undergo procedures as described below. Subjects will not be allowed to smoke cigarettes, as smoking is not allowed in the hospital or anywhere on the VCU campus. Subjects will have the option to use a nicotine patch dosed based on the amount of daily cigarettes smoked. Subjects will not be allowed to leave the CRS Unit nor receive visitors during their study visits. Subjects who are unable to comply with these restrictions will be dropped from the study. After a screening cocaine infusion to determine safety, eligible subjects will be randomized to Group A –placebo only or Group B –placebo followed by an ascending dose of lorcaserin. Six subjects will be assigned to Group A (placebo) and 12 subjects will be assigned to Group B (active lorcaserin).

Study Drug Dosage: Lorcaserin will be 10mg once daily increasing to 10mg twice daily.

Outcome Measures: The primary outcome measures are adverse events, cardiovascular responses (Heart rate (HR), blood pressure (BP), ECG measurements, subjective response to cocaine, cocaine self-administration, and cocaine blood PK. Secondary outcome measures will be impulsivity as measured by the immediate memory task (IMT).

- 1) Days 1-2: All subjects will be seen on the CRSU. All subjects will receive placebo on days 1-2 in a single blind fashion. Vital signs including heart rate, blood pressure and respiration rate will be obtained after placebo administration. Days 1-2 will be single-blind placebo, whereas all remaining study days will be double-blind. All subjects will leave the CRSU at the end of each study day.

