Meetings of the DSMB will be held at time points corresponding with annual progress reports. Open DSMB meetings will be attended by the PI, co-investigators, and research staff member (as appropriate). A closed DSMB session will be held at study completion and attendance will be limited to DSMB members and the PI. Meetings may be convened as conference calls as well as in person, although the initial meeting and meetings to discuss interim analysis will be face-to-face. An emergency meeting of the DSMB (open, closed, or executive session) may be called at any time by the Chairperson should questions of patient safety arise.

Issues discussed at DSMB sessions will include conduct and progress of the study, patient accrual, compliance with protocol, and problems encountered. As patient-specific data and treatment group data may be presented at DSMB sessions, the discussion will be regarded as completely confidential.

c. Conflict of interest

All participating investigators and DSMB members will declare any conflicts of interest before the study is initiated, annually, and in the event of changing circumstances. Beyond this, the investigators are blind to the conditions and the PI does not make active decisions about assignment or subject care or participation. This separation of activities diminishes the risk of harm to either science or subjects due to conflicts of interest.

d. Protection of confidentiality

All materials, discussions and proceedings of the DSMB are completely confidential. Members and other participants in DSMB meetings will be expected to maintain confidentiality.

e. Monitoring activities

After initial review and approval of the project, the monitoring activities of the DSMB will be to evaluate the progress of the trial, including periodic assessments of data quality and timeliness, participant recruitment, accrual and retention, participant risk versus benefit, performance of the trial site, and other factors that can affect study outcome.

f. Communication plans to IRB, NIDA, and FDA

The DSMB will make recommendations to the PI, who will then communicate the recommendations to the NIDA PO, and if necessary, to the FDA. Recommendations of the DSMB will be sent to the IRB as well.

STATISTICAL METHODS AND CONSIDERATIONS

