Prior to the analysis of the final study data, a detailed Statistical Analysis Plan (SAP) will be written describing all analyses that will be performed. The SAP will contain any modifications to the analysis plan described below.

Data Sets Analyzed

Initial analyses will evaluate group differences on demographic and baseline variables, will use contingency tables with chi-square testing, ANOVA's, and examination of correlations between baseline variables subjective responses and clinical results. General data analysis procedures: Urn randomization will be used for gender to reduce any potential between-group differences (lorcaserin vs. placebo) on baseline variables. Prior to data analysis procedures, groups will be examined for differences in other baseline characteristics that could potentially influence treatment outcome. Any variables that differ between groups and are related to outcome measures will be examined as potential covariates in subsequent data analyses.

Demographic and Baseline Characteristics

Women, minorities, and children (18-21 years of age) will be included to the extent they are reflected in this non-treatment seeking population. In our previous cocaine clinical trials, the percentage of females and males is approximately 30% and 70% respectively. We will continue recruitment efforts to achieve a 50-50 balance and thus permit meaningful analyses by sex across groups.

The ethnic representation has been 55% Black, 44% White, 15% Hispanic, and <1% Asian in previous research by our group. Nevertheless, we are prepared to implement recruitment procedures to ensure a more diverse patient population. These procedures include: 1) Targeted advertising in newspapers which serve minority communities (e.g., Hispanic or Latino communities). 2) Distribution of flyers and notices in neighborhoods known to have a high minority population. 3) Engaging in outreach activities on an ongoing basis, e.g.,

contacting church and community leaders in the Hispanic communities to provide educational material about cocaine dependence and its consequences; providing contact information to aid in referrals to our clinic.

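### The DSMB rules allow treatment-group data to be shown with the PI and staff present, and no PI-free session is assigned to the 50% safety look

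*Combined protocol and SAP*

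**What the plan says.** **Attendance and content of DSMB meetings (Data Safety Monitoring, item b).** On open meetings: "Open DSMB meetings will be attended by the PI, co-investigators, and research staff member (as appropriate"). On the scheduled closed session: "A closed DSMB session will be held at study completion and attendance will be limited to DSMB members and the PI". On content: "As patient-specific data and treatment group data may be presented at DSMB sessions, the discussion will be regarded as completely confidential". The Chairperson may also call an emergency meeting in open, closed or executive form; who attends is not stated. Meetings follow the annual progress reports, and those on the interim analysis are to be held in person.

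**The interim look (Interim Analysis, and the synopsis).** "When approximately 50% of patients have completed the study, an interim analysis for safety will be conducted by the DSMB". Whether that meeting is open or closed is not stated.

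**Blinding.** The Blinding section requires that "the identity of test and control treatments will not be known to investigators, research staff, or patients". The blind is lifted only after completion and database lock, emergencies excepted, and lorcaserin assays are held back until the end of the study. Item c of the DSMB section relies on the investigators being blind, and on the PI making no active decisions on subject care or participation, as a protection against conflicts of interest.

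**SAP timing (Statistical Methods and Considerations).** "Prior to the analysis of the final study data, a detailed Statistical Analysis Plan (SAP) will be written", and it may modify the analyses outlined in the protocol.

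**The concern.** Confidentiality is the only safeguard attached to group and patient-level data at DSMB sessions. It keeps information inside the room but does not blind the people in the room. In every type of session whose attendance the protocol defines, the PI is among those people.

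This matters because investigators go on making judgements after the interim:
- Adverse events are reported to the PI and graded for severity and relatedness to study drug, and they are listed among the primary outcome measures.
- The PI or a designee assesses lorcaserin side effects on Day 12.
- The investigator may discontinue treatment when this is judged to be in the subject's interest, and decides whether a protocol violation leads to withdrawal.
- Withdrawn subjects are replaced, so these decisions shape the final sample of a very small trial.

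These roles also weaken item c's assurance that the PI takes no active decisions on participation.

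**Working it through.** The plan gives no figure to reproduce on this point. The check sets the rules side by side, with supporting arithmetic on the interim sample.

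**Step 1. Which sessions exclude the PI?**

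| Session | PI present? | By-group data barred? |
|---|---|---|
| Open meeting | Yes, with co-investigators and staff | No |
| Closed session at study completion | Yes | No |
| Emergency closed or executive session | Not stated | No |
| Interim safety meeting at about 50% | Not stated | No |

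No row is stated to be PI-free. The protocol describes no separate open and closed reports, no masking of group labels, and no statistician with designated unblinded access. The text therefore permits by-group display to investigators before lock, which the Blinding section forbids.

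**Step 2. Size of the interim sample.** Inputs: 18 subjects, 6 placebo and 12 lorcaserin (Dosage/Dosage Regimen; Sample Size and Randomization); interim at about 50%.
- Interim n = 0.5 × 18 = 9.
- Expected placebo = 9 × 6/18 = 3; expected lorcaserin = 9 × 12/18 = 6.

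**Step 3. Would coded labels protect the blind?** Assume random order within a fixed 6/12 split; the urn scheme for gender is not modelled. The number of placebo subjects among 9 is then hypergeometric. Lorcaserin is the larger coded group when there are at most 4 placebo subjects.
- Total selections: C(18,9) = 48,620.
- Selections with 5 or 6 placebo: C(6,5)·C(12,4) + C(6,6)·C(12,3) = 6 × 495 + 220 = 3,190.
- P(at most 4 placebo) = 1 − 3,190/48,620 = 0.934.

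Anyone who picks the larger coded group as lorcaserin is right about 93% of the time, so relabelling the groups A and B gives little protection.

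**Step 4. What would the display reveal about later subjects?** With k placebo subjects among the first 9, the remaining 9 contain 6 − k placebo and 3 + k lorcaserin, so the chance that a given later subject is on lorcaserin is (3 + k)/9. At the expected k = 3 this is 6/9 = 2/3, the same as the design value 12/18. At k = 2 it is 5/9, and at k = 4 it is 7/9. The remaining totals may become known, but not who is in which group.

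**Side note on the inputs.** The randomization text describes "lorcaserin or placebo treatment groups in a 1:2 ratio", which read in order is the reverse of 12 lorcaserin and 6 placebo. These statements need reconciling. Steps 2 to 4 use the stated group counts; reversing them mirrors the arithmetic.

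**The case against.** The best reply is that the protocol says group data may be presented, not that they will be presented in an open meeting. Read charitably, the sentence could refer to closed sessions only, consistent with the strict control of the randomization code. The interim analysis is conducted by the DSMB, whose members are independent of the investigators and include a statistician. The first DSMB meeting is to establish monitoring guidelines and address operating procedures and the interim analysis plan, where session rules could be set.

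Part of this stands: the text leaves exposure possible and does not require it. But the attendance and data rules that are written down permit it, the documents that might close the gap are not included, and the PI helps to prepare the agenda for that first meeting.

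A reader might infer more than the documents support:
- *That every closed session includes the PI.* Only the scheduled one is stated to; emergency closed or executive sessions are also allowed.
- *That the PI's presence at the completion session exposes the interim look.* It does not. The exposure comes from having no PI-free session at the interim. The completion session matters only if it precedes database lock, and the order is not stated.
- *That the roughly 9 later subjects would be unblinded.* Step 4 shows that their individual assignments are not revealed.
- *That all primary outcomes are open to biased judgement.* Most are monitored HR and BP, the subject's own choices and VAS ratings, or assayed plasma cocaine. Adverse events are reported as summary statistics, not tested.
- *That the SAP will be written by people who have seen group data.* The protocol does not name its authors or say what they will have seen, and the main analyses are already outlined. The timing leaves this open, no more.

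**Conclusion.** The gap is real and should be closed before the interim look. The DSMB section, followed as written, permits the PI, co-investigators and staff to see by-group or individual data before database lock, in conflict with the Blinding section and with the DSMB section's own reliance on blind investigators.

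At the interim the data would cover about 9 subjects, expected 3 and 6. At that size coded labels would be guessed correctly about 93% of the time, assuming random order within a fixed 6/12 split, and staff who saw an event may recognise the subject behind a group-level line. The main exposure is in adverse event grading and relatedness, and in withdrawal and replacement decisions for subjects still under way. The amount of bias cannot be computed, because the documents do not say what will be shown, to whom, or how it would alter judgement.

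**What to change.** Amend item b of the Data Safety Monitoring section, and match it in any DSMB charter or operating manual:
1. Open sessions show only pooled or otherwise blinded data.
2. By-group or patient-level unblinded data, including at the 50% interim, are shown only in a closed session of DSMB members, including the board's statistician, without the PI, co-investigators or research staff.
3. The PI receives only the DSMB's written recommendation.
4. The PI does not attend any closed session held before database lock, including the completion session if it falls before lock.
5. As a low-cost safeguard, the SAP is finalised before any investigator or SAP author has access to by-group data.

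The board already has a statistician, so no new role is strictly needed, though unblinded access should be assigned explicitly. The cost is protocol and charter wording and separate open and closed reports; no subjects, visits or data are added.
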